### 11.5 Translational Endpoints

We assume that 90% of eligible patients will submit tissue and 80% of these will be successfully assayed. With 128 eligible patients enrolled on S1513, it is estimated that for each arm, 46 patients (n=92 total) will be included in analyses. The overall prevalence of each biomarker can be estimated to within 10% (95% confidence interval).

- a. The primary translational objective is to evaluate if *BRCA1* and *BRCA2* mutations (somatic or germline) are associated with improved clinical outcomes (OS, PFS, and ORR) in each treatment arm. Prevalences of *BRCA1* and *BRCA2* mutations in this patient population are estimated to be approximately 1-2% and 5-7%, respectively.
- b. Secondly, we will evaluate the impact of HRD positivity on clinical outcomes in each treatment arm. Although the HRD score threshold for positivity has yet to be determined in this disease, we will first dichotomize the score at its observed median value (represented as 50% prevalence in the tables below), and estimate the associations between that binary predictor and clinical outcomes. We will also assess the associations of HRD score as a continuous variable with clinical outcomes.
- c. Additionally, we will evaluate the impact of other exploratory genomic alterations (other than *BRCA1/2* mutations) identified by the BROCA-HR assay on clinical outcomes in each treatment arm.

We will evaluate if each potential biomarker is associated with the clinical outcomes of overall survival (OS), progression-free survival (PFS), and response rate (ORR) separately by treatment arm. The associations between each potential biomarker and both OS and PFS will be explored via Kaplan-Meier curves and Cox regression. We assume the baseline median OS is 6 months, 46 patients enrolled over 28 months and an additional 10 months of follow-up. The following table shows approximate power to detect OS hazard ratios of 2.5, 3, and 3.5, corresponding to median OS of 15, 18, and 21 months in the biomarker-positive subgroup, using a two-sided alpha of 0.1, for a range of biomarker frequencies.

| Biomarker Prevalence | Power  |        |          |
|----------------------|--------|--------|----------|
|                      | HR=2.5 | HR = 3 | HR = 3.5 |
| 5%                   | 30%    | 35%    | 39%      |
| 10%                  | 45%    | 54%    | 60%      |
| 25%                  | 73%    | 83%    | 89%      |
| 50%                  | 86%    | 93%    | 97%      |

Assuming a baseline median PFS of 3 months, the following table shows approximate power to detect PFS hazard ratios of 2.5, 3, and 3.5, corresponding to median PFS of 7.5, 9, and 10.5 months in the biomarker-positive subgroup, using a two-sided alpha of 0.1, for a range of biomarker frequencies.

| Biomarker Prevalence | Power    |        |          |
|----------------------|----------|--------|----------|
|                      | HR = 2.5 | HR = 3 | HR = 3.5 |
| 5%                   | 35%      | 43%    | 50%      |
| 10%                  | 54%      | 65%    | 73%      |
| 25%                  | 82%      | 91%    | 95%      |
| 50%                  | 91%      | 97%    | 99%      |

Assuming a null ORR of 10%, the following table describes the approximate power to detect differences in response rate of 25%, 30%, and 35% (corresponding to ORR of 35%, 40%, and 45%) in the biomarker-positive sub-group, using a two-sided 0.1 level test of proportions across a range of biomarker frequencies.

| Biomarker Prevalence | Power           |                 |                 |
|----------------------|-----------------|-----------------|-----------------|
|                      | $\Delta = 25\%$ | $\Delta = 30\%$ | $\Delta = 35\%$ |
| 10%                  | 20%             | 30%             | 39%             |
| 25%                  | 44%             | 56%             | 67%             |
| 50%                  | 50%             | 64%             | 76%             |

We also plan to estimate an HRD score threshold for positivity in this population by applying receiver operating characteristic curves, classifying patients by overall disease response. The precision of this estimate will depend not only on the number of patients with available data but also on the prevalence of disease response.

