The HRD assay is a next generation sequencing assay that targets ~54,000 SNPs which are evenly dispersed across the human genome. A by-product of this assay is the generation of 400 bp of sequence flanking each SNP location, resulting in a total of 21 Mb of genome sequencing data from each tumor sample analyzed. By cataloging the frequency of microsatellite repeat mutations and random somatic mutations within this 21 Mb of sequence data we are able to identify tumors with MSI or high somatic mutation burden due to underlying defects independent of MMR defects. In addition, the assay directly targets 43 genes known to be involved in DNA damage repair pathways and/or tumorigenesis, allowing the identification of both germline and somatic mutations within these genes (AKT1, ATM, ATR, BAP1, BARD1, BRCA1, BRCA2, BRIP1, CDK12, CHEK1, CHEK2, CTNNB1, ERCC4, FAM175A, FANCA, FANCD2, FANCE, FANCI, FANCL, KRAS, MLH1, MRE11A, MSH2, MSH6, MUTYH, NBN, PALB2, PIK3CA, PPP2R2A, PTEN, RAD50, RAD51, RAD51B, RAD51C, RAD51D, RAD52, RAD54B, RAD54L, RPA1, TP53, TP53BP1, XRCC2, XRCC3). Finally, hypermethylation of the *BRCA1* promoter has been proposed as a mechanism for *BRCA1* epigenetic inactivation, and will be evaluated in this assay.

One hundred thirty four PC samples derived from resected pancreatic tumors were analyzed (Dr. [REDACTED] collaboration). All samples were submitted as tumor cores from formalin fixed paraffin embedded (FFPE) tissue. Among 134 samples, 76 passed HRD analysis (failures were primarily to due to high non-tumor DNA content, > 70%). Approximately 7% of tumors carried *BRCA1/2/PALB2* deleterious mutations. Germline DNA was not available. Twenty other samples were analyzed from fine needle aspirate (FNA) specimens of patients with metastatic PC (Dr. [REDACTED] collaboration). Fifteen samples provided sufficient DNA for HRD analysis. 80% of samples (12/15) passed HRD analysis. Failures were due to high non-tumor content. For this metastatic sample study, the HRD score ranged from 11 to 46. Among the 15 evaluable samples, 4 showed other deleterious mutations: 3 *RAD52* mutations, and 1 *BRCA2* mutation (HRD score 46). HRD score range for both studies was 0 - 53. The distribution of scores in samples with *BRCA1/2/PALB2* mutations was lower than observed in breast/ovarian cancer, suggesting the cut-off may need to be < 42 in PC.

[figure not shown]

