#### 5.4 Specimen Submission Criteria

- a. Patients must be willing and able to undergo a biopsy after signed consent and prior to registration. Patients must have tumor tissue and blood samples available and be willing to submit tumor and blood samples as described in [Section 15.1](#).  
  
NOTE: Core biopsy required. FNA is not an acceptable substitute for core biopsy
- b. If archival tumor is available for submission, patients must be willing to submit tumor sample as described in [Section 15.1b](#).

- c. Patients must be offered the opportunity to participate in specimen banking for future use (see [Section 15.2](#)).

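### Is the 80% assay yield behind the 46 patients per arm in section 11.5 too optimistic for the HRD analysis?

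*Combined protocol and SAP*

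**What the plan says.** Section 11.5 (Translational Endpoints) starts from 128 eligible patients and states: "We assume that 90% of eligible patients will submit tissue and 80% of these will be successfully assayed". It arrives at 46 patients per arm, 92 in total, and uses that number for every biomarker. For HRD it says "we will first dichotomize the score at its observed median value (represented as 50% prevalence in the tables below"), so the 50% row of each power table is the HRD row. That row prints power of 86/93/97% for overall survival (OS) hazard ratios of 2.5, 3 and 3.5, and 91/97/99% for progression-free survival (PFS), at two-sided alpha 0.1. The score is also to be analysed as a continuous variable.

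The HRD Assay part of section 2.0 describes two pilot series. In the first, "One hundred thirty four PC samples derived from resected pancreatic tumors were analyzed", and "Among 134 samples, 76 passed HRD analysis". In the second, "Twenty other samples were analyzed from fine needle aspirate (FNA) specimens of patients with metastatic PC", with this result: "Fifteen samples provided sufficient DNA for HRD analysis. 80% of samples (12/15) passed HRD analysis".

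Section 5.4 requires a core biopsy before registration and adds that "FNA is not an acceptable substitute for core biopsy". The rationale for the translational work in section 2.0 classes the HRD assay as exploratory.

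**The concern.** The 80% has no cited source. The only 80% HRD pass rate in the documents is 12/15. That figure leaves out five aspirates without enough DNA, and it comes from a specimen type the trial refuses. Section 11.5 applies 80% to everyone who submits tissue. Counted that way, both pilots come out near 57-60%, and the confidence interval of the larger one excludes 80%.

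A single yield for two assays also looks odd, because section 18.4 gives a failure rate below 1% for BROCA-HR.

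If the HRD yield were really near 57%, the 50% row would overstate what the median split can detect, and a reader could take a null HRD result as stronger evidence than it is.

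**Working it through.** **The plan's n.** 128 × 0.90 × 0.80 = 92.2, or 46 per arm. This reproduces the stated figure. The denominator is explicit: the 80% applies to patients who submit tissue.

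**The plan's power.** The inputs are from section 11.5: 28 months of accrual, 10 months of follow-up, baseline median 6 months (OS) or 3 months (PFS), two-sided alpha 0.1. I assume exponential survival and uniform accrual. With λ = ln 2 / median, the probability of an observed event is

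p = 1 − [exp(−10λ) − exp(−38λ)] / (28λ)

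and power = Φ( ln HR / √(1/d1 + 1/d0) − 1.645 ), where d1 and d0 are the expected events in the biomarker-positive and biomarker-negative groups.

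For OS, HR 2.5 and a 50% split of 46 patients:
- p = 0.907 at median 6 months and 0.647 at median 15 months
- d0 = 23 × 0.907 = 20.8 (unrounded p) and d1 = 23 × 0.647 = 14.9
- ln 2.5 / √(1/14.9 + 1/20.8) = 2.70, so power = Φ(1.055) = 85.4%, against 86% printed

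The same formula matches all 24 printed OS and PFS cells to within 1 percentage point.

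**Pilot yields with exact 95% intervals.**
- Resected cores, all samples: 76/134 = 56.7% (47.9-65.2%)
- Aspirates, all samples: 12/20 = 60.0% (36.1-80.9%)
- Aspirates with sufficient DNA: 12/15 = 80.0% (51.9-95.7%)

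**Effect on the 50% row.**

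| Submission × yield | Total n | Per arm | OS power, HR 2.5/3/3.5 | PFS power, HR 2.5/3/3.5 |
|---|---|---|---|---|
| 90% × 80% (plan, printed) | 92 | 46 | 86/93/97% | 91/97/99% |
| 90% × 70% | 81 | 40 | 81/90/95% | 87/95/98% |
| 90% × 60% | 69 | 35 | 76/86/91% | 82/92/96% |
| 90% × 57% | 65 | 33 | 74/84/90% | 81/91/95% |
| 100% × 57% | 73 | 36 | 77/87/93% | 84/93/97% |

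The least favourable row loses 1 − 65.3/92.2 = 29% of the patients. The hazard ratio with the power computed for 2.5 at 46 per arm then becomes about 3.1 (OS) or 3.0 (PFS).

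The last row assumes that every eligible patient submits tissue. In that case 92 assayed patients need a yield of 92/128 = 72%, not 80%.

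I give no revised figures for response rate. Uncorrected, continuity-corrected and Fisher calculations all fail to match every row of the printed response table, so the method behind it is not known.

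**Do the pilots carry over to the trial?**
- The trial takes a core biopsy before treatment, from a primary or metastatic site (section 15.1). One pilot used cores from resected primaries; the other used aspirates.
- The resected-core failures were mainly from more than 70% non-tumour DNA. For the trial's HRD assay, section 18.4 has a pathologist review a stained slide and the areas densest in tumour scraped for extraction. The Background does not say whether the pilot cores were handled this way.
- The five aspirates lost for insufficient DNA reflect a specimen type the trial excludes. Section 18.4 allots five to ten 10-micron slides to HRD, for an assay needing 50-200 ng of DNA.

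**The case for a change.** The strongest case for a change is that no HRD series in the documents supports 80% of all submitted tissue as a point estimate. The larger series has an interval ending at 65%, and the only matching 80% uses a narrower denominator. HRD is the second translational aim, with printed power and a planned threshold estimate, and a range in one row of the tables would cost little.

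Part of this stands. The 80% is unsourced, and it is favourable when set against the pilots on the all-samples count. The arithmetic in the 57% and 60% rows is correct.

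Three parts do not stand:
- The plan does state its denominator, and that 12/15 is the origin of the 80% is only a guess.
- The 60% figure has an interval that reaches 80% and includes losses specific to aspirates, so the case rests on one series in a different specimen type.
- The BROCA-HR failure rate is listed as analytical performance, for tissue with at least 20% tumour. It is not shown to be a yield from all submitted biopsies, so it is not a like-for-like comparison with the HRD pilots.

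**Conclusion.** No change is needed. The stated n and the OS and PFS power follow from the stated assumption, and the documents do not show that assumption to be wrong for the trial's own biopsies. It is a planning guess at the favourable end of what the pilots show, and a sponsor could reasonably defend it given tumour enrichment, the exclusion of aspirates, and tissue submission as a condition of eligibility (section 5.4).

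If the least favourable pilot yield applied at 90% submission, the HRD split would have about 33 patients per arm. Power for a hazard ratio of 2.5 would be about 74% (OS) and 81% (PFS). For hazard ratios of 3 and 3.5, power would still be 84% and 90% for OS, and 91% and 95% for PFS. These figures rest on exponential survival and the plan's own medians, accrual and follow-up.

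The consequence is small. HRD is exploratory, the tables are described as approximate, and neither enrolment nor the primary OS analysis uses this number. The number actually assayed in each arm will be known at analysis, and a null HRD result would then be judged by its confidence interval, not by power planned beforehand. Citing a source and showing a range would improve the planning text without altering what is analysed or how.

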### **HRD Assay**

The homologous recombination deficiency (HRD) assay developed by Myriad Genetics (myChoice HRD™) combines genomic patterns of loss of heterozygosity (LOH) "footprint", telomeric allelic imbalance (TAI), and large-scale state transitions (LST) scores as an indicator of HR deficiency

regardless of mechanism. (94,95,96) The HRD assay is a DNA-based, next generation sequencing assay that detects tumors with the HRD phenotype. The assay main components include the HRD score and somatic *BRCA1/2* mutations. Deleterious or suspected deleterious somatic mutations in *BRCA1/2* define a tumor as having the HRD phenotype (regardless of HRD score). The HRD score is the sum of its three individual components: 1) LOH score is the number of LOH regions of intermediate size (> 15 Mb and < whole chromosome), 2) LST score is the number of chromosome breaks points (translocations, inversions or deletions) in adjacent segments of DNA of at least 10Mb, 3) TAI score is the number of regions with allelic imbalance which extend to the subtelomere but do not cross the centromere. The HRD Score is the unweighted sum of LOH, TAI and LST measurements on a scale from 0-100. The three HRD components demonstrate significant correlation with each other (correlation coefficients 0.77 and 0.83). Although highly correlated, the three scores contain different information and combining them generates a more robust predictor of HRD. (97,98) Based on molecular data further tested in clinical trials, HRD positive tumors (breast and ovarian cancers) were those with an HRD score of  $\geq 42$  or a deleterious mutation in *BRCA1/2* gene. Although the primary clinical application of the HRD score will be to enrich for responders to HR targeted therapies, this was not the criteria for selecting the threshold. A threshold has not been yet described in PC. Response is highly dependent on the treatment regimen and activity of a specific drug. In contrast, a threshold based on the underlying biology of the tumor, i.e., HRD, should be independent of treatment effect. Establishing a predefined threshold value based on the biology of HRD, rather than a specific treatment outcome, allows the validation of the test to be conducted independent of the effect of a specific therapy.

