***BRCA1* and *BRCA2* testing**

*BRCA1* and *BRCA2* (*BRCA1/2*) are tumor suppressor genes, in which inherited loss-of-function mutations confer a higher lifetime risk of breast and ovarian carcinoma, as well as an increased risk of pancreatic adenocarcinoma (standardized incidence ratios (SIR) 3.5-5.8 for *BRCA2*, and SIR 4.1 for *BRCA1* mutations, respectively). (4,5,6,7) *BRCA1/2* are key components of the *BRCA*-Fanconi anemia (FA) pathway, which is critical to homologous recombination (HR)-mediated DNA repair.

PARP enzymes recognize DNA damage and facilitate DNA repair to maintain genomic stability. Preclinical studies demonstrate that PARP inhibition in the presence of *BRCA* deficiency leads to synthetic lethality. (8) PARP inhibitors (i) have shown preclinical and clinical activity in targeting tumors with pre-existing DNA repair defects, in particular *BRCA1* and *BRCA2* deficient advanced breast, ovarian, and pancreatic tumors. (9,10,11,12,13,14,15,16,17,18)

In addition to BRCA1/2 mutations, many genes involved in homologous recombination may be altered by mutation, rearrangement, DNA methylation or attenuated mRNA expression and can result in impairment of the HR pathway. It is speculated that if other factors beyond germline BRCA mutations are comprehensively evaluated, 20-25% of pancreatic cancers will demonstrate HR deficiency (HRD phenotype) or BRCAness. (19,20)

Preclinical evidence suggests that MLH1 loss, RAD51 mutations, and ERCC1 loss may particularly enhance cytotoxicity from PARP inhibition plus irinotecan/SN38 combination. (21,22,23) It is not yet known whether BRCA1/2 mutations will sensitize pancreatic cancer to treatment with irinotecan and PARP inhibitors.

The secondary aim of this randomized Phase II study is to investigate whether the addition of a PARP inhibitor (ABT-888) to irinotecan-based therapy (mFOLFIRI) will improve response, progression free survival (PFS), and overall survival (OS) for patients with germline or somatic BRCA1/2 mutation-associated pancreatic cancers. Thus, gBRCA1/2 and somatic tumor BRCA1/2 testing for the entire study cohort is an essential integrated biomarker.

Exploratory translational aims will assess whether BRCAness or HRD phenotype (by BROCA-HR and the HRD assay described previously in [Section 18.4a](#)) correlate with response, PFS and OS in each treatment arm.

The current design for BROCA-HR includes the following genes (n=75):

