**The expected distribution of the biomarker in the study population:**

It is estimated that 7-10% of the study population will demonstrate deleterious germline or somatic *BRCA1/2* mutations. Cutpoints will not be used for *BRCA* testing. Test results will be described as deleterious germline or somatic mutation “present” or “absent”. In *gBRCA* or somatic *BRCA* mutation-positive patients median PFS of 3 months is assumed for Arm 2 (FOLFIRI) that improves to 5 months for Arm 1 (mFOLFIRI + ABT-888).

It is estimated that 20-25% of the study population will demonstrate germline or somatic alterations in other BROCA-HR panel genes or evidence of “genomic scarring” by SNPs analysis.

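### Does the 50% power row overstate what the median split of the HRD score can detect?

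*Combined protocol and SAP*

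**What the plan says.** Section 11.5, item b, notes that no HRD cutoff has been settled for this disease. The plan is therefore that "we will first dichotomize the score at its observed median value (represented as 50% prevalence in the tables below". The next sentence adds a second analysis: "We will also assess the associations of HRD score as a continuous variable with clinical outcomes". At the end of 11.5 there is a third: "We also plan to estimate an HRD score threshold for positivity in this population by applying receiver operating characteristic curves".

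The OS table in 11.5 is for 46 patients per arm and a two-sided alpha of 0.10. Its hazard ratios of 2.5, 3 and 3.5 are described as "corresponding to median OS of 15, 18, and 21 months in the biomarker-positive subgroup", against a baseline median of 6 months. The 50% row reads 86%, 93% and 97%, and the 25% row 73%, 83% and 89%. The 50% row of the PFS table reads 91%, 97% and 99%.

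On prevalence, the HRD Assay background says "A threshold has not been yet described in PC". Appendix 18.4 speculates that "20-25% of pancreatic cancers will demonstrate HR deficiency (HRD phenotype) or BRCAness". For the other sequencing assay it says "It is estimated that 20-25% of the study population will demonstrate germline or somatic alterations in other BROCA-HR panel genes" or scarring, and separately estimates 7-10% with BRCA1/2 mutations. The rationale for the biomarker work in Section 2.0 classes the HRD assay as exploratory.

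**The concern.** A median cut yields 50% positives whatever the biology. If only 20-25% of tumours are HR-deficient and only they have longer survival, then even with perfect ranking 50-60% of the upper half is HR-proficient, and the hazard ratio between halves falls well short of 2.5-3.5. The median split is listed first and is the only HRD analysis tied to a power figure. A null result read against 86-97% power could then be taken as evidence that the score is uninformative, when dilution might explain it. Since these biomarkers are meant to inform later Phase III trials, that misreading would matter. The apparent remedy is to make the continuous score the lead analysis and qualify the 50% row.

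**Working it through.** **Inputs from Section 11.5.** n = 46 per arm; accrual 28 months plus 10 months of follow-up; baseline median OS 6 months; two-sided alpha 0.10 (critical value 1.645).

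**Step 1: reproduce the printed 50% row.** With exponential survival, hazard λ = ln 2 / median and uniform accrual, the probability of an observed death is 1 − (e^(−10λ) − e^(−38λ)) / (28λ).

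- Baseline (6 months): 0.9065, so 23 × 0.9065 = 20.85 deaths.
- Positive group at HR 2.5 (15 months): 0.6466, so 23 × 0.6466 = 14.87 deaths.
- SE of the log hazard ratio = √(1/20.85 + 1/14.87) = 0.339.
- Power = Φ(ln 2.5 / 0.339 − 1.645) = Φ(2.70 − 1.645) = 85.4%.

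The same calculation gives 93.2% at HR 3 and 96.6% at HR 3.5. The plan prints 86/93/97%. The method reproduces all 24 cells of the OS and PFS tables within 2 points, so the table contains no arithmetic error.

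**Step 2: dilute the effect.** Two assumptions are needed that the protocol does not make for this analysis: only the top share p of scores carries the hazard ratio, and the score ranks tumours perfectly. The upper half then holds a fraction 2p of carriers, so the average log hazard ratio between halves is roughly 2p × ln(HR). For p = 25% and HR 2.5:

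- Hazard ratio between halves ≈ exp(0.5 × 0.916) = 1.58.
- Expected deaths = 46 × (0.75 × 0.9065 + 0.25 × 0.6466) = 38.7.
- Power ≈ Φ(0.458 × √38.7 / 2 − 1.645) = Φ(−0.22) = 41%.

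**Step 3: simulate both analyses.** At least 20,000 runs per cell, normal score; log-rank test on the sample-median split against a Cox score test on the continuous score. Null rejection was 10-11% for both, so the comparison is fair. OS power, median split v continuous:

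| Share carrying the effect | HR 2.5 | HR 3.5 |
|---|---|---|
| 20% | 32% v 46% | 44% v 63% |
| 25% | 41% v 53% | 58% v 72% |
| 35% | 62% v 64% | 80% v 83% |
| 40% | 70% v 67% | 87% v 85% |
| 50% | 76% v 68% | 92% v 87% |

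At HR 3 and 20-25% the figures are 39-51% v 56-64%. In the last row the median split falls below the printed 86% and 97% because the sample median does not fall exactly at the population cut. For PFS at 20-25%: 37-47% v 52-60% at HR 2.5, and 52-66% v 71-79% at HR 3.5.

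**Step 4: how firm is the 20-25%?** Adding the 7-10% BRCA1/2 estimate without overlap gives 20 + 7 = 27% to 25 + 10 = 35%. Over that range OS power is 46-62% v 56-64% at HR 2.5, so the gap shrinks from about 10 points to about 2.

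**Step 5: imperfect ranking.** With an assumed correlation of 0.7 between the score and the trait that carries the effect (a figure the documents do not give) and 20-25% carriers, OS power is 23-28% v 30-34% at HR 2.5 and 32-38% v 41-47% at HR 3.5. Both analyses are then weak.

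**Step 6: score shape.** The documents give only ranges, among them "For this metastatic sample study, the HRD score ranged from 11 to 46". With a strongly right-skewed score (lognormal, sigma 1) and HR 2.5, the median split is level at 30% carriers (52% v 50%) and ahead at 35% (61% v 49%). A dozen or so samples cannot settle the shape.

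**The case for a change.** The case for acting is that the 50% comes from the cut and is not an estimate of prevalence. Every prevalence figure in the documents lies below it, and no power is given for that situation. At 20-25% carriers the median split would miss a real effect 42-68% of the time (100 − 58 to 100 − 32). One sentence would warn readers, at no cost in patients or assays. Rank coding would also remove the dependence on skew: at HR 2.5 it gives 45/54/67/71% at 20/25/35/40% carriers, against 32/41/61/70% for the median split.

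The arithmetic stands, and so does the point that a null median split would be weak evidence against the score. Three things limit it.

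- The row states its own condition. The diluted hazard ratios between halves, 1.46-1.85, lie outside the 2.5-3.5 for which power is quoted, and any power table is lower for smaller effects.
- Confining the effect to HR-deficient tumours is an outside assumption, and perfect ranking fits poorly with the HRD Assay background, where a deleterious BRCA1/2 mutation defines the phenotype whatever the score.
- Rank coding is a preference: it gives a hazard ratio per rank, which is harder to interpret, and loses 5-10 points if the true step is exactly at the sample median. The plan does not fix how the continuous score is coded, so analysts remain free to use ranks.

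**Conclusion.** No change is needed. The 50% row is right for the full hazard ratio between the two score halves, which is what the text beside it states. If only 20-25% of tumours carry the effect, with perfect ranking and a normal score, OS power is about 32-58% for the median split and 46-72% for the continuous score.

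That does not justify reordering the analyses. The continuous score is already planned alongside the median split. Section 11.5 sets no hierarchy, alpha allocation or decision rule among the HRD analyses, so naming a lead would have no inferential effect. Nor is the continuous score uniformly better on the raw scale: it gains 2-3 points at 35% carriers and loses 2-3 points at 40% and 5-8 points at 50%. With the cutoff unknown, running both is a fair trade-off.

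A sentence saying that power falls when fewer than half of tumours carry the effect would be true, but it would alter no analysis, result or decision. An analyst reporting an exploratory within-arm null can say so from the table's stated hazard ratios. The primary OS test, the sample size and the type I error are unaffected.

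### The appendix aim of testing whether adding ABT-888 helps BRCA1/2-mutated patients has no planned analysis, because Section 11.5 evaluates markers only within each arm

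*Combined protocol and SAP*

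**What the plan says.** Objectives 1.3a to 1.3c ask whether BRCA1/2 mutations, the HRD score and other BROCA-HR alterations relate to outcome in each treatment arm. Section 11.5 follows them: it evaluates every marker against "overall survival (OS), progression-free survival (PFS), and response rate (ORR) separately by treatment arm", using Kaplan-Meier curves and Cox regression, and makes the within-arm BRCA association the primary translational objective.

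Section 18.4b, on BRCA1 and BRCA2 testing, asks something else. The study's secondary aim there is to "investigate whether the addition of a PARP inhibitor (ABT-888) to irinotecan-based therapy (mFOLFIRI) will improve response", PFS and OS "for patients with germline or somatic BRCA1/2 mutation-associated pancreatic cancers", and this is the stated reason for testing the whole cohort. For mutation-positive patients, Section 18.4 on the expected distribution of the biomarker says "median PFS of 3 months is assumed for Arm 2 (FOLFIRI) that improves to 5 months for Arm 1 (mFOLFIRI + ABT-888" (the closing bracket follows).

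On frequency, Section 18.4 says: "It is estimated that 7-10% of the study population will demonstrate deleterious germline or somatic" BRCA1/2 mutations. Section 11.5 has BRCA1 and BRCA2 prevalences "estimated to be approximately 1-2% and 5-7%, respectively".

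For HRD and BRCAness, Section 18.4b asks only whether they "correlate with response, PFS and OS in each treatment arm". The arm comparisons in Sections 11.2 and 11.4 are not restricted by marker, and Section 1.2 does not list the BRCA arm comparison among the secondary objectives.

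**The concern.** The aim in Section 18.4b is a treatment effect in a marker-defined subgroup: Arm 1 against Arm 2 among BRCA-positive patients. Section 11.5 plans a marker effect within a treatment arm. These are different contrasts. A marker that is purely prognostic is associated with outcome in both arms although ABT-888 works no better in one marker group than the other. The aim and its 3 versus 5 month assumption therefore feed no estimate, test or power figure.

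The background says the biomarker work should inform future Phase III trials and identify who benefits most. It also predicts that HR-proficient cancers gain nothing significant from the PARP inhibitor. Those statements are rationale, not listed objectives, but they too are between-arm questions. If the contrast is not named in advance, a reader may compare significance across arms and take an association seen only in Arm 1 as evidence of a predictive marker.

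**Working it through.** **Model.** Exponential survival, uniform accrual over 28 months, 10 months of further follow-up (Section 11.5), no dropout. With median m and λ = ln 2/m, the chance that a patient has an event is P(m) = 1 − (e^(−10λ) − e^(−38λ))/(28λ). This gives P(3) = 0.985, P(5) = 0.937, P(6) = 0.907, P(15) = 0.647. Power = Φ(ln HR / SE − 1.645), where SE² is the sum of 1/events over the groups compared (two-sided 0.1).

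**The plan's own figures.**
- Patients: 128 × 0.9 × 0.8 = 92.2, or 46 per arm, as stated.
- OS table, 10% prevalence, HR 2.5: 4.6 × 0.647 = 2.97 events in positives and 41.4 × 0.907 = 37.5 in negatives. SE = 0.602, power 45%; the plan says 45%.
- All 24 OS and PFS cells reproduce within 1 point as marker-positive versus marker-negative in a single arm of 46. The tables therefore say nothing about the ABT-888 effect in BRCA-positive patients.

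**BRCA arm comparison, PFS 3 versus 5 months (HR 5/3 = 1.67).** Adding the Section 11.5 prevalences (assuming no overlap) gives 6-9%; Section 18.4 gives 7-10%. I use 6-10% with an equal split between arms.

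| Patients with a BRCA result | Prevalence | BRCA-positive | Events | Power | 95% CI if 1.67 is observed |
|---|---|---|---|---|---|
| 92 | 6% | 5.5 | 5.3 | 14.5% | about 0.30 to 9.1 |
| 92 | 10% | 9.2 | 8.8 | 18.8% | about 0.45 to 6.2 |
| 128 | 6% | 7.7 | 7.4 | 17.1% | |
| 128 | 10% | 12.8 | 12.3 | 22.7% | |

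For 80% power, 4 × (1.645 + 0.842)² / (ln 1.67)² ≈ 95 events would be needed. BRCA status is not a stratification factor, so the split can be uneven. With 46 per arm and binomial counts, some arm has 0 or 1 positive patient in about 40% of trials at 6% prevalence and 9% at 10%. In simulation (6,000 trials per prevalence) the ordinary Cox hazard ratio was not finite in 36.8% (6%) to 9.8% (10%) of trials. A Firth-penalised one was estimable in 89.1% to 98.5%.

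**HRD median split, interaction.** Assume an arm ratio of 1.67 to 2.0 in HRD-high and 1.0 in HRD-low, 23 patients per cell. For PFS at 1.67, events are 23 × 0.937 = 21.5 in one cell and 23 × 0.985 = 22.65 in each of the other three, so SE = 0.423 and power is 33%. Over both ratios, power is 33-49% for PFS and 31-46% for OS.

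**Reading significance across arms.** For a purely prognostic split the chance of significance in Arm 1 but not Arm 2 is p1(1 − p2), where p1 and p2 are the within-arm powers. With no arm effect, PFS ratio 1.67 gives 0.521 × 0.479 = 25%, and ratio 2.0 gives 0.739 × 0.261 = 19%. Over both endpoints and an arm effect of 1.0 or 1.5, ratios 1.67-2.0 give about 19-25%. The plan's own ratios give about 12, 6 and 3% (OS) and 8, 3 and 1% (PFS) at 2.5, 3 and 3.5. In simulation at ratios 1.67-2.0, an interaction test gives a false signal in that direction in 5-6%.

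**The case against.** The strongest reply is that Objectives 1.3a to 1.3c and Section 11.5 agree with each other and govern, and that the needed quantities are nearly there. The two arms are independent, so subtracting the two within-arm log hazard ratios, with their standard errors, gives the interaction. Kaplan-Meier curves by BRCA status within each arm would display the medians that Section 18.4 assumes. This stands in part. A reader might infer that a marker significant in one arm only is the sole sign of prediction the plan can yield; that is not so. What is missing is the named contrast and its interval.

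A reader might also take 19-25% as the plan's general rate of misleading findings. It is not. It depends on the ratios assumed, falls to about 1-12% at the plan's own ratios, shows no clear excess over the interaction test at 3 or above, and applies to a decision rule the plan never states.

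Nor do the documents support extending the contradiction to HRD or BRCAness: Section 18.4b keeps those aims within arm, and the background classes them as exploratory.

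Finally, a BRCA estimate from a handful of patients will be very imprecise. That argues for saying so beside the aim, not for leaving an aim and an effect assumption without an analysis.

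**Conclusion.** The point holds for BRCA1/2: the documents state a between-arm aim and an effect size for it, and plan no matching analysis. The aim's rank also conflicts, being secondary in Section 18.4b, absent from Section 1.2, and replaced by a within-arm question in Sections 1.3a and 11.5.

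The contrast has about 14-19% power with 92 assayed patients. The 17-23% upper case assumes that up to 128 have a BRCA result. Blood is mandatory and the stated BROCA failure rate is below 1%, but a germline result alone would miss somatic mutations. All figures assume exponential survival, planned numbers and an equal split; uneven counts lower them (12-18% averaged over random counts with 92 assayed).

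For HRD, naming an interaction is a worthwhile improvement, not the repair of a contradiction. This should be changed, but the primary OS comparison does not depend on it.

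**What to change.** 1. Reconcile the secondary-aim label in Section 18.4b with Sections 1.2, 1.3 and 11.5 by calling the BRCA arm comparison exploratory.
2. Add to Section 11.5, for BRCA1/2 and for estimation only: counts, events and Kaplan-Meier curves by arm; ORR by arm with exact intervals; and a Firth-penalised Cox hazard ratio, Arm 1 versus Arm 2, with a profile-likelihood interval where estimable. If an arm has no positive patient, report counts only.
3. State that the 3 versus 5 month contrast has about 14-19% power with 92 assayed and about 17-23% with up to 128 (two-sided 0.1, 6-10% prevalence, equal split), and that the table ratios are within-arm contrasts.
4. For the HRD score (median split and continuous), report a treatment-by-marker interaction from a Cox model over both arms, stratified by prior systemic treatment for metastatic disease, with arm hazard ratios and intervals by marker group. Label it exploratory and unadjusted for multiplicity, and give the median-split power of about 31-49% at assumed ratios 1.67-2.0. Do the same for the mutation/LOH composite only if its LOH cutoff, which the documents do not give, is fixed first.

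Keep the within-arm analyses. The cost is analysis-plan wording on data already planned, low power, and a few more exploratory estimates. The Revision #1 memo says accrual is closed and patients are off treatment, so fix the text before markers are linked to outcome, or label the analyses post hoc. Merely rewording Section 18.4 to match Section 1.3 would remove the contradiction but leave the between-arm question unanswered.
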